APPENDIX III: USUAL CARE – PATIENT FOLLOW-UP SURVEY

You have been given a booklet to complete for this study. The booklet contains some questions related to visits with your surgeon, about what was important to you when you thought about your decision for breast cancer surgery, and any materials that helped you make a decision. Your answers will help us to better understand how to support patients in making their decision about breast cancer surgery.

1. Directions on how to complete each set of questions are written on the top of each set.
2. You will be given the site coordinator's name and telephone number. You can call any time with any concerns or questions.
3. It is very important that you return the booklet to us.
4. Please hand the completed survey to the site coordinator or use the stamped and addressed envelope provided to mail the completed survey to the site coordinator. If we do not hear from you in the next week, we will contact you again.

Thank you for taking the time to help us.

PATIENT FOLLOW-UP (T2) SURVEY— USUAL CARE

Thank you for taking the time to complete this survey. This survey is about 50 questions and should take about 10 to 20 minutes to complete.

The first set of questions contains items that are related to visits with a surgeon. Please answer each statement to the best of your ability.

	Not at all confident (1)	(2)	(3)	(4)	Very confident (5)
1. How confident are you in your ability to know what questions to ask a surgeon?					
2. How confident are you in your ability to get a surgeon to answer all of your questions?					
3. How confident are you in your ability to make the most of your visit with a surgeon?					
4. How confident are you in your ability to get a surgeon to take your chief health concerns seriously?					
5. How confident are you in your ability to get a surgeon to do something about your chief health concern?					

The second set of questions contains items that are related to your recent visit with your surgeon. Surgeons have different styles in how they interact with patients and we would like to know more about how you felt about your visit with your surgeon. Please indicate how much you agree or disagree with each statement. Please answer to the best of your ability.

	Strongly disagree (1)		Neutral (4)		Strongly agree (7)	
	(2)	(3)	(5)	(6)		
6. I feel that my surgeon has provided me choices and options.						
7. I feel understood by my surgeon.						
8. I am able to be open with my surgeon at our meetings.						
9. My surgeon conveys confidence in my ability to make treatment choices.						
10. I feel that my surgeon accepts me.						
11. My surgeon has made sure I really understand about my condition and what I need to do.						
12. My surgeon encourages me to ask questions.						
13. I feel a lot of trust in my surgeon.						
14. My surgeon answers my questions fully and carefully.						
15. My surgeon listens to how I would like to do things.						
16. My surgeon handles people's emotions very well.						
17. I feel that my surgeon cares about me as a person.						
18. I don't feel very good about the way my surgeon talks to me.						
19. My surgeon tries to understand how I see things before suggesting how to do things.						
20. I feel able to share my feelings with my surgeon.						

The next set of questions asks about some facts that surgeons think are important for patients to know about breast cancer. The correct answer to each question is based on medical research. Please answer to the best of your ability.

21. For most women with early breast cancer, how much would waiting a few weeks to make a treatment decision affect their chances of survival?

- A little or not at all
- A lot
- Some

22. With treatment, about how many women diagnosed with early breast cancer will eventually die of breast cancer?

- About half will die of breast cancer
- Most will die of breast cancer
- Most will die of something else

23. After which treatment is it more likely that women will need to have another operation to remove more tumor cells?

- Lumpectomy
- Mastectomy
- Equally likely for both

24. On average, which women with early breast cancer live longer?

- Women who have a mastectomy
- Women who have a lumpectomy and radiation
- There is no difference

25. On average, which women have a higher chance of having cancer come back in the breast that has been treated?

- Women who have a mastectomy
- Women who have a lumpectomy and radiation
- There is no difference

We are interested in what was important to you when you made the decision about breast cancer surgery. We asked you these same questions before you met with your surgeon, and are asking again to see if anything has changed. Please mark on a scale from 0 to 10, how important were each of the following to you as you make your decision about surgery.

How important was it to you to . . .

	Not at all important										Extremely Important
26. keep your breast?	0	1	2	3	4	5	6	7	8	9	10
27. remove your entire breast to gain peace of mind?	0	1	2	3	4	5	6	7	8	9	10
28. avoid having radiation	0	1	2	3	4	5	6	7	8	9	10

29. (*Now that your clinic visit is over, if you currently have a preference to treat your early stage breast cancer*), which treatment do you prefer?

- I am not sure
- Lumpectomy and radiation
- Lumpectomy only
- Mastectomy
- Other surgery

Other surgery: _____

30. Do you feel sure about the best choice for you?

- Yes
- No

31. Do you know the benefits and risks of each option?

- Yes
- No

32. Are you clear about which benefits and risks matter most to you?

- Yes
- No

33. Do you have enough support and advice to make a choice?

- Yes
- No

The next questions ask about any materials that helped you prepare to meet with your surgeon and make a decision for breast cancer surgery.

34. Did you review any information after seeing your surgeon?

- Yes
- No

If you answered “No” to question #34, please proceed directly to question #35.

(If yes), what types of information did you review after meeting your surgeon?

(If yes), how much time did you spend reviewing the information?

- Less than 15 minutes
- 15 - 60 minutes
- More than 1 hour

If you answered “Yes” to question #34, please proceed directly to question #36.

If you answered “No” to question #34, please answer question #35.

35. Did you receive any information at any time?

- Yes, I reviewed information (either before or after seeing the surgeon).
- No, I did not review any information.

If you answered “Yes” to question #35, please answer question #36.

If you answered “No” to question #35, please proceed directly to question #48.

	Not at all	A little	Somewhat	Quite a bit	A great deal
36. Did the information help you recognize that a decision needs to be made?	1	2	3	4	5
37. Did the information prepare you to make a better decision?	1	2	3	4	5
38. Did the information help you think about the pros and cons of each option?	1	2	3	4	5
39. Did the information help you think about which pros and cons are most important?	1	2	3	4	5
40. Did the information help you know that the decision depends on what matter most to you?	1	2	3	4	5
41. Did the information help you organize your own thoughts about the decision?	1	2	3	4	5
42. Did the information help you think about how involved you want to be in this decision?	1	2	3	4	5
43. Did the information help you identify questions you want to ask your surgeon?	1	2	3	4	5
44. Did the information prepare you to talk to your surgeon about what matters most to you?	1	2	3	4	5
45. Did the information prepare you for a follow-up visit with your surgeon?	1	2	3	4	5

46. Where did you review the information? Check all that apply.

- On my own computer at home
- On a computer at my family or friend's home
- On my own tablet or mobile phone
- On my family or friend's tablet or mobile phone
- On a public computer (ex. library)
- On a iPad in clinic
- Other

(If other), specify _____

47. Did anyone else review the information? (Either with you or you sending them the information)

- Yes
- No

(If yes), who? Check all that apply.

- Partner/spouse
- Family member

(If family member), specify _____

- Friend
- Other

(If other), specify _____

The following questions are for all patients, regardless of whether they did or did not review any materials to help make a decision about the type of breast cancer surgery to have.

48. Would you like to receive information from the clinic?

- Yes
- No

49. What do you think would be the best format for you to receive and review information from the clinic?

- Paper version
- Computer-based version
- DVD-based version
- Other

(If other), specify _____

50. If the clinic sent web-based material prior to the first appointment with the surgeon, what would be the best way to receive this information?

- By email
- By electronic medical record, such as using a patient portal (MyChart)
- By text
- By mail
- Other

(If other), specify _____

Below are some questions so we can learn a little more about you. This information will help us understand how decision making between the surgeon and patient may be differ between patients, and how to better support patients in making their decision about breast cancer surgery.

1. What is the **highest** level of school or degree you have completed?

- Some high school or less
- High school diploma or GED
- Vocational degree or some college
- College degree
- Graduate school degree or higher

2. Are you of Hispanic, Latino, or Spanish origin?

- Yes
- No

3. How would you describe your racial background?

- White or Caucasian
- Black or African American
- Asian
- American Indian or Alaska Native
- Native Hawaiian or other Pacific Islander
- Other

(If other), specify _____

4. What do you consider to be your primary language?

- English
- Spanish
- Other

(If other), specify _____

5. What is your current marital status?

- Single, never married
- Married or domestic partnership
- Widowed
- Divorced
- Separated

6. What is your household annual income?

- <\$25,000 per year
- \$25,000 - \$49,999 per year
- \$50,000 - \$99,999 per year
- >\$100,000 per year

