1.5.3 Use of a general-use decision aid

Because we are conducting this research in clinics that serve a high proportion of socioeconomically disadvantaged patients but that also care for patients in other socioeconomic strata, we are using a general-use decision aid. Using the same decision aid for the entire clinic population increases the feasibility and sustainability of the intervention. However, a critical part of the study is to evaluate the effectiveness of this decision aid for patients from different backgrounds.

The tool we selected was developed collaboratively by the Informed Medical Decisions Foundation and Health Dialog.^{35,55} Originally created as a DVD, it was converted to a web-based platform based on user feedback requesting flexibility in mode of delivery. The web-based decision aid utilizes static, didactic information written for an 8th grade reading level, and video clinical vignettes to promote consideration of personal values and preferences. It includes modules for invasive cancer, non-invasive cancer, and reconstruction. It has been used successfully in academic and community settings to increase knowledge and decrease decisional conflict.^{35,43,44,48} The greatest gains in knowledge were seen in patients with lower educational backgrounds.³⁵

Preliminary data: In our pilot study, we randomized patients to receive either the Health Dialog web-based decision aid, or links to standard websites, prior to the surgical consult; pre-consult knowledge was assessed. Knowledge was higher in patients who received the decision aid versus the standard websites (70% vs. 60%, p=0.004). These findings were unchanged after adjusting for sociodemographic characteristics.

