10.1.4.4 Patient, Surgeon and Clinic Characteristics

- Patient characteristics

We will abstract patient demographic (age, race, zipcode+4 to calculate ADI, payer), clinical (AJCC stage, estrogen/progesterone receptor and HER2neu) and treatment factors (surgery, radiation, systemic therapy, hormonal therapy) from medical records.

The zipcode+4 will be used to calculate the Area Deprivation Index (ADI) score. The ADI represents an area-based measure of socioeconomic deprivation based on 17 Census-based markers of socioeconomic status. A publicly available dataset provides an ADI score for each zipcode+4 in the United States. The raw ADI score will be transformed into a 20 category quantile-based measure (every 5th percentile) using national ADI thresholds. After the transformation into the categorical variables, the raw zipcode+4 and the raw ADI score will be destroyed.

- Surgeon characteristics

We will obtain gender, race, ethnicity, fellowship training, percent of practice that is breast, and years in practice. This will be included in the baseline survey.

- Clinic characteristics

We will obtain number of staff, presence of a navigator, annual breast cancer volume, and payer mix. This will be collected by each site's coordinator.

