Here, y_{ijk} denotes the response of the i^{th} level-1 unit (patient) of the j^{th} level-2 unit (surgeon) of the k^{th} level-3 unit (clinic). The variable x_{ijk} ($=0, 1$) denotes the intervention status of patient i from surgeon j within clinic k . The variables t_1 ($=1, 2, 3, 4, 5, 6, 7$) and t_1^2 ($=1, 4, 9, 16, 25, 36, 49$) are the linear and quadratic terms for wave with the corresponding coefficients β_1 and β_2 representing the fixed linear and quadratic effects to model the underlying secular trend. The variable z ($=0, 1$) denotes if patient i was enrolled during the post-COVID restart time period for a given clinic with the corresponding fixed effect coefficient β_3 . The variable t_2 ($=0, 1, 2, 3, 4, 5, 6$) denotes if patient i was enrolled within the first wave post-COVID restart time period ($t_2 = 1$); within the second wave post-COVID restart time period ($t_2 = 2$); and so on through the sixth wave post-COVID restart time period ($t_2 = 6$). The maximum value is $t_2 = 6$ because when the stepped-wedge design was suspended all clinics were at least enrolling part way in wave 2 of the possible 7 waves. For patients enrolled prior to the post-COVID restart time period the value of $t_2 = 0$. The random effect u_k is the level-3 (clinic) random intercept effect (random clinic variance); the random effect $u_{j(k)}$ is the level-2 random intercept effect for

the $j(k)^{th}$ level-2 unit (random surgeon variance nested in clinics); the random effect $e_{i(j(k))}$ is the random individual variance within surgeons nested in clinics. The term β_0 is the intercept. The term θ represents the intervention effect of the decision aid and is the primary effect of interest.

Models will adjust for the a priori specified patient characteristics described above that are likely to be strongly predictive of the endpoints. In the event that the approximately continuous outcomes PEPPi-5 self-efficacy and Active Patient Participation Behaviors are not approximately symmetrically distributed, variable transformation will be considered (e.g., square-root transformation). Further, as part of the planned efficacy analysis we will fully test the variance-covariance structure of the model, while blinded to any treatment effects, which may lead to a more parsimonious model.

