12.1.2 Sample Size and Power Calculations

Co-Primary Objective #1: Based on current patient enrollment, we estimate a sample size of 563 patients. This has been reduced from our original estimate of 1,050 patients. We assume 23 surgeons will participate. Aim 1 has two primary endpoints: PEPI-5 self-efficacy and Active Patient Participation Behaviors (count). We desire a family-wise two-sided Type I error rate of $\alpha=0.05$; under a Bonferroni correction, tests will be conducted with nominal of $\alpha=0.05/2 = 0.025$.

Using the revised analysis model and updated accrual projections, we estimated Fisher's information for the regression parameters when the study will have complete data; inverting that information we obtained an estimate of the standard error for the intervention effect parameter, thereby computing minimally detectable Cohen's-*D* effect size for each primary endpoint at 80% and at 90% power. As a sensitivity analysis, we considered varying estimates of ICCs to ensure robust findings.

Self-Efficacy: Assuming PEPI-5 has a standard deviation (SD) of 4.3 and both within-surgeon and within-site-between surgeon ICC of 0.07, we will have 80% power to detect effects as small as $0.55*4.3=2.4$ and 90% power to detect effects as small as $0.63*4.3=2.7$ on a scale of 5-25. We consider a difference of 2 points to be clinically meaningful.

Active Patient Participation Behaviors: Assuming the active patient participation behavior count has a standard deviation of 23.1 and a within-surgeon ICC of 0.01 and within-site-between surgeon ICC of 0.0001, we have 80% power to detect a difference of $0.50*23.1=11.6$ and 90% power to detect a difference as small as $0.57*23.1=13.2$ on a 0-150 scale. We consider a difference of 10 to be clinically meaningful.

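### The adjustment promised in 12.1.1 points to a record-based list that omits education, although education is collected with PEPPI-5; it should be named as a covariate

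*Combined protocol and SAP*

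**What the plan says.** The model in 12.1.1 (Co-Primary Objective #1) has an intervention indicator, wave and wave squared, a post-COVID restart indicator, time since restart, and clinic and surgeon random effects. After the equation the section adds: "Models will adjust for the a priori specified patient characteristics described above that are likely to be strongly predictive of the endpoints". Section 12 contains no list of patient characteristics before that sentence.

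The nearest earlier description is 10.1.4.4: "We will abstract patient demographic (age, race, zipcode+4 to calculate ADI, payer", followed by clinical and treatment factors, all taken from medical records. Education is not in that list, in the table of patient measures (10.1.5) or in the model equation.

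Education is nevertheless collected. The closing block of the follow-up survey in Appendices III, IV and V opens with a five-level item on highest schooling. The booklets give the purpose of the block as: "This information will help us understand how decision making between the surgeon and patient may be differ between patients". PEPPI-5 is items 1-5 and the knowledge questions are items 21-25 of the same booklets.

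The background treats education as relevant. Section 1.5.2 counts limited education as part of socioeconomic disadvantage, and 1.5.3 says of this decision aid: "The greatest gains in knowledge were seen in patients with lower educational backgrounds".

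**The concern.** An analyst who follows the cross-reference arrives at a list with a neighbourhood index of deprivation but no individual measure of education. Education is a stable trait that the decision aid cannot change, so asking for it after the consultation does not make it a post-treatment covariate. Because it shares a booklet with PEPPI-5 and knowledge, it is available, apart from skipped items, for the women who have those outcomes.

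Two things are at stake. The first is precision: a covariate that predicts the outcome lowers the standard error of the intervention effect, which matters more now that the expected sample is 563 and no longer 1,050. The second is case mix. Different women are enrolled before and after crossover, and coordinators identify whom to approach (8.1, 8.2.1). Clinic and surgeon effects absorb stable differences between sites, and the wave and restart terms absorb common trends. None of them absorbs a change in education within a clinic that coincides with its crossover. The log of women who decline research (8.2.1) records age, race, ethnicity and insurance but not education, so it would not reveal such a change.

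**Working it through.** **Inputs from 12.1.2.** Two-sided alpha 0.025 per endpoint; 563 patients; PEPPI-5 SD 3.4 (Wave 1 update) or 4.3 (the other calculation given); detectable difference 0.55 SD at 80% power and 0.63 SD at 90%; 2 points taken as clinically meaningful. **Assumed, not in the documents:** R², the share of PEPPI-5 variance that education explains beyond the other covariates, set at 1% to 10%.

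**Step 1. Reproduce the plan's figures.** 0.55 × 3.4 = 1.87 and 0.63 × 3.4 = 2.14. The implied standard error is 1.87 / (2.2414 + 0.8416) = 0.607 points from the 80% figure and 2.14 / (2.2414 + 1.2816) = 0.607 from the 90% figure, so the two agree. The 0.55 itself cannot be rebuilt, because accrual by clinic and wave and the restart dates are not given. A generalised least squares check with equal cells (563/60), 23 surgeons, and ICC 0.07 at both levels or at clinic level only gave 0.50-0.55 SD in six of seven assumed restart patterns and 0.81-0.84 SD in the other. I therefore take 0.55 as given.

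**Step 2. Effect on precision.** The detectable difference is multiplied by √(1 − R²). Power at 2 points is Φ(2 / (0.6065 × √(1 − R²)) − 2.2414). The equivalent number of extra patients is 563 × (1/(1 − R²) − 1).

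| Assumed R² | √(1 − R²) | Detectable at 80% (points) | Power at 2 points | Equivalent extra patients |
|---|---|---|---|---|
| 0 | 1.000 | 1.87 | 85.5% | 0 |
| 1% | 0.995 | 1.86 | 85.8% | 6 |
| 2% | 0.990 | 1.85 | 86.2% | 12 |
| 5% | 0.975 | 1.82 | 87.3% | 30 |
| 10% | 0.949 | 1.77 | 89.1% | 63 |

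With SD 4.3, power at 2 points starts at 64.3% and rises to between 64.8% and 69.4% over the same range. The scaling is approximate: it treats the variance reduction as proportional at all levels and education as roughly unrelated to intervention status given the other terms.

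**Step 3. Size of a case-mix bias, if one occurred.** Bias = √R² × 3.4 × shift in education in SD units. For an assumed shift of 0.2 SD that the other terms do not absorb: √0.01 × 3.4 × 0.2 = 0.07 points, and √0.10 × 3.4 × 0.2 = 0.22 points, or roughly 3% to 11% of the 2-point difference. To give the shift a scale: in the pilot (1.5.1) 34% had less than a college degree, so the SD of that indicator is √(0.34 × 0.66) = 0.474, and 0.2 SD is about 9.5 percentage points.

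**The case against.** **The plan does not exclude education.** This stands. The sentence in 12.1.1 names no covariates, and 10.1.4.4 cannot sensibly be the full covariate set, because it includes surgery, radiation and systemic therapy, which follow the consultation. A reader might infer that the plan has decided to forgo education; the text supports only that education is unnamed. The covariates have to be named in any case, and education then has to be put in or left out.

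**Nothing links education to PEPPI-5.** This also stands. The statement in 1.5.3 concerns knowledge gains, and 1.5.2 only defines disadvantage. A reader might infer that education is a strong predictor of self-efficacy; the documents give no such association, and the upper end of the R² range has no source in them.

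**A shift at crossover is hypothetical.** Section 8.3 keeps consent, consultation and survey procedures identical after crossover. Section 8.1 sets surgeon-proportional targets, training and monthly reports. ADI, race and payer, if adjusted for, would carry part of any shift. So a reader should not infer that the comparison is biased; the adjustment is a safeguard.

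**Why education and not another variable?** The same block asks income, marital status and primary language, and these are equally absent from 10.1.4.4; they can be settled when the list is written. The Brief Health Literacy Screen is asked before the consultation and is available for non-responders to the follow-up survey. In the intervention period, however, it is asked after the decision aid has been sent, so it is less clearly unaffected by the intervention than education.

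**Missing data.** Education sits at the end of a booklet of about 50 questions and is absent whenever the follow-up survey is absent. That argues against using it in the main audio-count model or in the planned weighting for survey non-response. It is a minor cost for PEPPI-5 and knowledge.

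**Conclusion.** The point holds in a limited form. The promised adjustment has no named covariates, the list it most nearly refers to omits the woman's own education, and education is already collected beside two of the outcomes. Naming it is worthwhile because it costs almost nothing. At R² of 1% to 2% the improvement in power is under one percentage point; at 10% it is 3.6 points (89.1% − 85.5%). Under SD 3.4 the 80% detectable difference is already below 2 points without education, so no design conclusion changes. The case-mix protection is real in principle, but its size depends on a shift that no document reports.

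**What to change.** Before outcomes are analysed by intervention status:

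- In 10.1.4.4, add education from the follow-up booklet to the patient characteristics and state its source.
- In 12.1.1, name education as a fixed covariate in the PEPPI-5 and knowledge models, and fix its coding in advance: the five booklet levels, or college degree or more versus less.
- Leave education out of the main audio-count model, or use it there only in a sensitivity analysis.
- For skipped education items among survey responders, use the multiple imputation already planned in 12.1.4 for missing predictors.

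If the team prefers to leave education out, 12.1.1 should say so and give the reason. The cost is a sentence or two of text, 1 to 4 degrees of freedom and a small amount of item non-response. No new data, visits or patients are needed.
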